7.3 Exclusion Criteria

1. Patients with other skin conditions that might interfere with AD diagnosis and/or evaluation (such as psoriasis or current active viral, bacterial and fungal skin infections) as assessed by the investigator.

2. Patients who have used systemic treatments (other than biologics) that could affect AD less than 4 weeks prior to baseline visit (Day 0), e.g. retinoids, methotrexate, cyclosporine, hydroxycarbamide (hydroxyurea), azathioprine and oral/injectable corticosteroids. Intranasal corticosteroids and inhaled corticosteroids for stable medical conditions are allowed.
3. Patients who have used any topical medicated treatment for AD two weeks prior to start of treatment/ Baseline (Day 0), including but not limited to, topical corticosteroids, tars and bleach.
4. Patients who use topical products containing urea, ceramides or hyaluronic acid two weeks prior to Baseline.
5. Patients who use anti-histamines for AD within 2 weeks of baseline. Non-sedative anti-histamines for other indications may be used throughout the study provided the patient is on a stable dose for 4 weeks prior to Baseline.
6. Patients with the presence of an active or chronic allergic reaction as evidenced by an irregular white cell count determined by eosinophils $> 0.3 \times 10^9 /L$ at the screening visit.
7. Patients who have had excessive sun exposure, have used tanning booths or other ultraviolet (UV) light sources four weeks prior to Baseline (Day 0) and/or are planning a trip to a sunny climate or to use tanning booths or other UV sources between screening and follow-up visits.
8. Patients who have a history of hypersensitivity to any substance in DS107 capsules or placebo capsules.
9. Patients who have any clinically significant controlled or uncontrolled medical condition or laboratory abnormality that would, in the opinion of the investigator, put the patient at undue risk or interfere with interpretation of study results.
10. Patients who have a clinically significant impairment of renal or hepatic function.
11. Patients with significant uncontrolled cardiovascular, neurologic, malignant, psychiatric, respiratory or hypertensive disease, as well as uncontrolled diabetes and floride arthritis or any other illness that, in the opinion of the investigator, is likely to interfere with completion of the study.
12. Patients with chronic infectious disease (e.g., hepatitis B, hepatitis C or infection with human immunodeficiency virus).

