8 STUDY CONDUCT

8.1 Study Schedule

During the study, six visits to the clinic are scheduled at least one week after the screening visit: one at the start of the comparative treatment period/baseline (Day 0/Visit 2) and five in the comparative treatment period (Week 2/Visit 3, Week 4/Visit 4, Week 6/Visit 5 and Week 8/Visit 6). A final safety follow-up visit (Visit 7) will be conducted two weeks after Visit 6 or two weeks after the final visit attended if the patient does not complete the study. The baseline visit must be performed, at the latest 30 days after the screening visit.

Patients who discontinue the study early will be asked to attend the investigative site as soon as possible so that assessments scheduled for Visit 6 can be conducted at an Early Termination visit.

In the event that treatment is occurring, a wash out period of up to 4 weeks may be necessary. At the Screening visit, after giving informed consent to participate, patients will be assessed using the screening examinations. Eligible patients with confirmed AD using the Hanifin and Rajka criteria and who meet all the inclusion criteria and do not meet the exclusion criteria at the baseline visit will be enrolled.

During the treatment period and follow-up period patients will be restricted from using any other treatment for AD, with the exception of the same emollients they have been consistently using at the baseline visit. Any medication (prescription as well as OTC drugs) or therapeutic intervention deemed necessary for the patient, and which in the opinion of the Investigator do not interfere with the safety and efficacy evaluations, may be continued. A list of ‘medications and therapeutic regimens excluded from the study’ is defined below (Section 9.2.11.2).

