8.2.1 Screening Visit (Visit 1)

The patient must sign and date the ICF before any study-specific procedures are conducted.

Once informed consent has been obtained, the investigator will assign a Patient Number (as per Section 10.5) and the following screening procedures/assessments will occur:

- Demographic data
- Medical / Surgical history (as detailed in Section 9.2.1)
- Assessment of inclusion/exclusion criteria (Sections 7.2 & 7.3)
- Hanifin and Rajka criteria review (as detailed in Appendix 2 [15.2])
- Samples for clinical laboratory safety tests (haematology, serum biochemistry, urinalysis and FSH levels (when applicable) as detailed in Section 9.2.4)
- Sample for pregnancy test (only female patients of child-bearing potential, as detailed in Section 9.2.5)
- Vital signs (blood pressures, heart rate and body temperature), as detailed in Section 9.2.3)
- Physical examination (as detailed in Section 9.2.2)
- Body Mass Index (as detailed in Section 9.2.6)
- Body Surface Area (as detailed in Section 9.1.4)
- Investigator’s Global Assessment (as detailed in Section 9.1.1)
- Eczema Area and Severity Index (EASI) (as detailed in Section 9.1.2)

- NRS Pruritus Assessment (as detailed in Section 9.1.3)
- Concomitant medication assessment (as detailed in Section 9.2.11)

Unscheduled visits may occur when a patient needs to make a visit in between the scheduled visit dates due to an adverse event (AE), difficulty complying with the study protocol requirements, or a significant change in their disease state. All procedures that are medically necessary should be followed.

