An NRS for the assessment of pruritus will be captured on a daily basis from baseline through to the follow up visit. Emollient use will also be captured on a daily basis for the same period.

Collection of AE's will begin after the first administration of IMP has occurred.

On completion of this visit, patients will be advised that they will be required to return to the investigational site at Visit 3 and to bring with them the unused DS107 capsules/Placebo patient packs, the used DS107 capsules/Placebo patient packs, and the patient compliance log.

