9.1.3 Pruritus NRS

Severity of pruritus related to AD will be self-assessed by patients daily using the NRS (Appendix 5). Patients will be asked to estimate the intensity of pruritus at its worst over the previous 24 hours. The Pruritus NRS is a single-question assessment tool that will be used to assess the patient's worst itch as a result of AD in the previous 24 hours. Patients will score their pruritus due to AD on a scale of 0 – 10, with 0 (no itch) and 10 (worst itch imaginable) (Phan et al. 2012). Patients will complete the rating scale at screening and then daily starting at baseline through to the last study visit.

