day will be ignored and the between-visit daily average will be computed using non-missing values only. The baseline value will be the average computed during the screening period. This analysis of change from baseline in NRS will be performed the same as the analysis of change from baseline in EASI, with CFB_NRS and B_NRS representing the change from baseline in NRS and the baseline NRS, respectively.

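### The SAP baselines pruritus NRS on a screening-period average, but only one NRS score is scheduled before Day 0, so the literal baseline is a single score up to 30 days old

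*SAP*

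**What the plan says.** SAP 2.2.12.2 treats NRS as a daily measure. The value at each visit is the mean of the non-missing daily scores gathered after the preceding visit. For baseline it says: "The baseline value will be the average computed during the screening period". Change from this baseline is the response, and the baseline is also a model covariate.

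The protocol's collection schedule is different. Section 9.1.3 says: "Patients will complete the rating scale at screening and then daily starting at baseline through to the last study visit". Section 8.2.1 lists one NRS assessment at Visit 1. Section 8.2.3 lists one at Visit 2 and adds: "An NRS for the assessment of pruritus will be captured on a daily basis from baseline through to the follow up visit". The flow chart in Appendix 1 agrees, with a single mark at screening and a continuous line from Visit 2.

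On timing, Protocol 8.1 says that "six visits to the clinic are scheduled at least one week after the screening visit" and that "The baseline visit must be performed, at the latest 30 days after the screening visit". The flow chart and SAP 2.2.5 put the screening visit anywhere from Day -30 to Day -1.

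SAP 2.1 has a general baseline rule, the last non-missing value before dosing, but it gives way wherever something else is specified. For NRS, something else is specified.

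**The concern.** The NRS rule describes an average that the collected data cannot supply. It overrides a general rule that would have worked. A programmer must then choose what the sentence means, and the choices give different baselines for the same patient.

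The literal choice is the screening score alone, which may not reflect the condition in which the patient enters the trial. Protocol 8.1 notes: "In the event that treatment is occurring, a wash out period of up to 4 weeks may be necessary". Section 7.3 excludes topical AD medication in the two weeks before Day 0 and systemic AD therapy in the four weeks before. Section 7.2 asks for at least 7 days of stable emollient use before baseline, which may begin after screening. A screening score can therefore have been taken on treatment that was later stopped, or before the emollient was started.

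At stake are the within-arm changes (summary tables and LS means) and the usefulness of the covariate for a named secondary endpoint. EASI follows the general rule and is normally baselined at Visit 2. The literal reading would leave NRS baselined at an earlier visit than EASI, although the SAP says the two are analysed in the same way.

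**Working it through.** The documents give no sample size, power or precision figure for NRS, so there is no planned figure to reproduce. The check is a count of scores, their age, and the consequence of each reading.

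**1. Scheduled scores before the first dose**
- Before Day 0: one, at Visit 1 (Protocol 8.2.1, 9.1.3, Appendix 1).
- On Day 0: one at Visit 2 (Protocol 8.2.3). It is pre-dose, because Protocol 8.2.3 places the first dose after the baseline visit and SAP 2.2.5 places it after all baseline assessments.
- Each post-baseline interval holds about 14 daily scores.

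**2. Age of the screening score at Day 0**
- Protocol 8.1: 7 to 30 days.
- Flow chart and SAP 2.2.5: 1 to 30 days.
- Eligible patient still on topical AD medication at screening: 14 to 30 days (two-week exclusion plus the 30-day limit).
- Eligible patient still on systemic AD therapy at screening: 28 to 30 days (four-week exclusion plus the 30-day limit).
- Patient with no washout and already on emollient: possibly only 7 days, taken under trial conditions.

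**3. Possible readings of the baseline sentence**
1. The screening score alone. This fits a screening window that ends at Day -1.
2. The mean of the screening and Day 0 scores, if the between-visit averaging rule is applied at Visit 2 and the screening-visit score is counted.
3. The Day 0 score alone, if the same rule is applied without counting the screening-visit score. This equals the SAP 2.1 rule.

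**4. Within-arm shift**
Let S and D be the arm means at screening and Day 0, P the later mean, and d = D - S. Here d is an assumption; the documents do not give it.
- Reading 1: P - S = (P - D) + d
- Reading 2: P - (S + D)/2 = (P - D) + d/2
- Reading 3: P - D, no shift

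If a fraction f of patients drift by 1 point, then d = f:

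| f | Reading 1 | Reading 2 | Reading 3 |
|---|---|---|---|
| 25% | 0.25 | 0.125 | 0 |
| 50% | 0.50 | 0.25 | 0 |
| 100% | 1.00 | 0.50 | 0 |

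All these scores precede randomised treatment, so the expected shift is the same in every arm and cancels in the between-arm contrast.

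**5. Precision (illustrative; all correlations assumed)**
Let rs and r0 be the correlations of the screening and Day 0 scores with later NRS, and rho the correlation between those two scores, with equal variances. The adjusted-variance ratio against a Day 0 baseline is:
- Reading 1: (1 - rs²)/(1 - r0²)
- Reading 2: (1 - r²)/(1 - r0²), with r = (rs + r0)/√(2(1 + rho))

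| rs, r0 | Reading 1 | Reading 2, rho = 0.3 / 0.5 / 0.8 |
|---|---|---|
| 0.5, 0.5 | 0% | -18% / -11% / -4% |
| 0.4, 0.5 | +12% | -8% / -3% / +3% |
| 0.3, 0.5 | +21% | +1% / +5% / +10% |
| 0.3, 0.6 | +42% | +8% / +14% / +21% |

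For example, for (0.3, 0.6) under reading 1: (1 - 0.09)/(1 - 0.36) = 0.91/0.64 = 1.42.

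**6. Day 0 in the Week 2 average**
The SAP does not say whether the day of the preceding visit counts. If it does not, Day 0 contributes nothing. If it does, a pre-dose score is 1 of 15 values (1/15 = 6.7%; 1/17 to 1/13, or 5.9% to 7.7%, across the ±2-day window).

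**The case against.** The strongest reply is that the literal reading is only one candidate. The documents never define a screening period; Day -30 to -1 is a visit window. The baseline sentence directly follows the between-visit averaging rule, and that rule applied at Visit 2 would use the Day 0 score. The rule is also not impossible to compute, since a mean of one score is still a number. These points have force: the text is ambiguous as well as mismatched to the schedule. But they show that the plan does not fix one value per patient, and neither the literal reading nor the two-score mean gives the average described.

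Second, the between-arm comparison is what the endpoint is about, and it is not biased. This stands and is why the point is minor.

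Third, Protocol 8.2.3 rechecks at Visit 2 that the severity inclusion criteria still hold, so as to remove patients who responded to emollient. This is a partial safeguard against improvement drift. It does not test NRS and does nothing about worsening after washout.

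Fourth, the precision figures rest on assumed correlations. Under reading 1 they cannot be favourable, because every set assumes that screening correlates no better than Day 0. That is right; they show only that the direction is unsettled.

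Finally, averaging both pre-dose scores is defensible and could be more precise than Day 0 alone (by up to 18% in variance in the table). True, but it brings back half of any drift, and the plan would have to state it.

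**Conclusion.** Wrong as written, minor. The SAP's NRS baseline does not match the protocol's collection schedule. Its literal result is one 24-hour-recall score, 7 to 30 days old under Protocol 8.1, with the pre-dose Visit 2 score not used as baseline. The mean change within each arm then carries the whole screening-to-Day 0 drift, or half of it under the two-score reading. The size and sign of that drift are not in the documents: itch could worsen after washout or ease with emollient. The effect on precision is likewise unknown. That the between-arm contrast is unbiased rests only on all candidate scores preceding randomised treatment. The mismatch itself rests on the documents alone and needs none of the assumed values.

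**What to change.** Replace the baseline sentence in SAP 2.2.12.2 with: *Baseline NRS is the last non-missing NRS score recorded before the first dose, as in SAP 2.1 (normally the Day 0 score at Visit 2, otherwise the screening score); pre-dose scores are excluded from the Week 2 interval average.*

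Two additions help. State as a limitation that a single-day baseline is compared with a mean over roughly 14 days. Say also that the Week 2 average starts the day after Visit 2: a separate Day 0 entry made by the patient may not be placeable before or after the first dose, and this removes the question.

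The cost is a short SAP edit before unblinding. Both scores are already collected, so no protocol amendment is needed, and the screening fallback keeps patients whose Day 0 score is missing. If the sponsor prefers the mean of the two pre-dose scores, the SAP should name those two scores explicitly and accept the d/2 shift.

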2.2.12.3 Exploratory Endpoints

- Time to response by Week 8. A Kaplan-Meier lifetable will be constructed using nominal visits. A Wilcoxon-Gehan test will be used to compare all treatments; p-values will also be computed for each of the three treatment pairs for the primary endpoint using the FAS population. This will be a graph.
- Probability of being in response (PBIR) between Weeks 2 and 8. The PBIR will be computed as a descriptive statistic for the primary endpoint using the FAS population. Each visit will be equally weighted in this analysis. This will be a graph.
- Sustained efficacy between Weeks 8 and 10. This analysis will be endpoint-specific. Binary endpoints will be evaluated using logistic regression (PROC LOGISTIC) controlling for baseline IGA score and baseline AD severity while continuous endpoints will be analyzed using proc GLM controlling for the same factors. A shift table will be created presenting the number and frequencies of subjects in response and the shift from Week 8 to Week 10 for the primary endpoint analysis for both the FAS and PPS populations.
- Change from baseline in the Dermatology Life Quality Index (DLQI) score in treated population compared to placebo population at Week 2, 4, 6, 8 and 10 and from Week 8 to Week 10 and change from baseline to subject's last treatment visit.

DLQI is a set of 10 questions, scored 0=Not at all, 1=A little, 2=A lot, or 3=Very much, or 0=Not relevant, except for Questions 1 and 2 that do not include a response of 'Not Relevant'. Missing responses are assigned '0'. The DLQI total score is calculated by summing the score of each question resulting in a maximum of 30 and a minimum of 0. The higher the score, the more quality of life

is impaired. This scoring will be done by the data management group and provided to CTDS in the SDTM datasets.

Mean DLQI will be computed as the Total DLQI divided by the number of questions with non-missing responses. The scoring instructions for DLQI specify that if 2 or more questions are not answered, then the questionnaire will not be scored; this approach is not taken here with Mean DLQI computed instead. Summary statistics for Total DLQI and Mean DLQI will be presented. The analysis of change from baseline in Mean DLQI will be performed the same as the analysis of change from baseline in EASI, with appropriate changes in the variables for change from baseline and Mean DLQI at baseline.

Summary statistics as continuous data and change from baseline will be presented by treatment group and visit for the totals for the 4 sub-scales:

Symptoms and feelings	Questions 1 and 2
Daily Activities	Questions 3 and 4
Leisure	Questions 5 and 6
Personal relationships	Questions 8 and 9

- Change from baseline in the Patient Orientated Eczema Measure (POEM) score in treated population compared to placebo population at Week 2, 4, 6, 8 and 10 and from Week 8 to Week 10 and change from baseline to subject's last treatment visit.

POEM is a set of 7 questions regarding the frequency of conditions related to eczema, with responses of 0 = no days, 1 = 1-2 days, 2 = 3-4 days, 3 = 5-6 days, or 4 = every day. The sum of the scores for the 7 questions is the Total POEM.

Mean POEM is the Total POEM divided by the number of questions with non-missing responses. The scoring instructions for POEM specify that if response to one question is missing, the response for that question will be equated to 0, and if the responses to more than one question are missing, then the questionnaire is not scored; this approach is not taken here with Mean POEM for questions with non-missing responses computed instead. The analysis of change from baseline in Mean POEM will be performed the same as the analysis of change from baseline in EASI, with appropriate changes in the variables for change from baseline and Mean POEM at baseline.

Summary statistics (counts and frequencies) will be presented by treatment group and visit for categories based on Total POEM of

Clear or almost clear = 0 to 2;

Mild eczema = 3 to 7;

Moderate eczema = 8 to 16;

Severe eczema = 17 to 24;

Very severe = 25 to 28.

Shift tables presenting the number and frequency of subjects in each eczema severity category at Week 8 and last treatment visit and Week 8 to Week 10 will be presented by treatment group.

- Change from baseline in the Patient Global Impression of Severity (PGI-S) score in treated population compared to placebo population at Week 2, 4, 6, 8 and 10 and from Week 8 to Week 10 and change from baseline to subject's last treatment visit.

The categories for the PGI-S are: normal, mild, moderate or severe. A Shift table will be created presenting the number and frequencies of subjects in each category and the shift from the follow-up visit to baseline.

Patient Global Impression of Change (PGI-C) is captured at the follow-up visits and is a 7 –point scale assessing the overall status of the patient since the start of the study with responses of 1=very much improved, 2=much improved, 3=minimally improved, 4= no change, 5=minimally worse, 6= much worse and 7=very much worse. Summary statistics (count and frequencies) will be presented by treatment group and visit for the status categories. A shift table presenting the number and frequency of subjects in each category at Week 8 to Week 10 will be presented by treatment group.

- Plasma DGLA concentrations in treated population compared to placebo population at Baseline/Day 0, Week4, Week 8 and Week 10: samples to be retained for the potential analysis at a later date. Details of these analyses will be described in a separate document and the analyses will not be included with the analyses described herein.

- Determination of AD biomarkers in treated population compared to placebo population at Baseline/Day 0 and Week8/Early Termination (samples to be retained for the potential analysis at a later date). Details of these analyses will be described in a separate document and the analyses will not be included with the analyses described herein.

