9.1.5 Dermatology Life Quality Index (DLQI) Questionnaire

The effect of AD on patient quality of life will be self-assessed by the patient at Baseline/Visit 2, Week 2/Visit 3, Week 4/Visit 4, Week 6/Visit 5, Week 8/Visit 6/ET and Follow up Week 10/Visit 7 using the DLQI (Appendix 6) developed by Finlay and Khan (1994)

DLQI has a maximum value of thirty based on the patients response to ten questions scored according to the following scale:

- Very Much = 3
- A lot = 2
- A little = 1
- Not at all = 0
- Not relevant = 0

- Question unanswered = 0
- Question 7: “prevented work or studying” = 3

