15.7 Appendix 7: Patient Orientated Eczema Measure

Patient ID #: ____ - ____

Patient Initials: ____

Visit Day: _____

Visit Date (dd-mmm-yyyy): _____

Please circle one response for each of the seven questions below about your eczema. Please leave blank any questions you feel unable to answer.

1. Over the last week, on how many days has your skin been itchy because of your eczema?

No days 1-2 days 3-4 days 5-6 days Every day

2. Over the last week, on how many nights has your sleep been disturbed because of your eczema?

No days 1-2 days 3-4 days 5-6 days Every day

3. Over the last week, on how many days has your skin been bleeding because of your eczema?

No days 1-2 days 3-4 days 5-6 days Every day

4. Over the last week, on how many days has your skin been weeping or oozing clear fluid because of your eczema?

No days 1-2 days 3-4 days 5-6 days Every day

5. Over the last week, on how many days has your skin been cracked because of your eczema?

No days 1-2 days 3-4 days 5-6 days Every day

6. Over the last week, on how many days has your skin been flaking off because of your eczema?

No days 1-2 days 3-4 days 5-6 days Every day

7. Over the last week, on how many days has your skin felt dry or rough because of your eczema?

No days 1-2 days 3-4 days 5-6 days Every day

© CR Charman, AJ Venn, HC Williams, December 2004.

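### DLQI totals, DLQI sub-scale totals and POEM severity categories are reported however many items are blank, so forms with skipped items can look milder than they are

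*SAP*

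**What the plan says.** **DLQI.** SAP 2.2.12.3 sums ten items, "resulting in a maximum of 30 and a minimum of 0", and states "Missing responses are assigned '0" for blanks. Protocol 9.1.5 agrees: "Question unanswered = 0". The SAP then cites the instrument's rule and sets it aside: "if 2 or more questions are not answered, then the questionnaire will not be scored; this approach is not taken here". In its place, "Mean DLQI will be computed as the Total DLQI divided by the number of questions with non-missing responses", and the change-from-baseline model uses this mean. The total is not dropped: "Summary statistics for Total DLQI and Mean DLQI will be presented". Four two-item sub-scale totals, and their changes from baseline, are also summarised by arm and visit.

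**POEM.** The SAP cites a rule under which one missing item counts as 0 and more than one leaves the form unscored. It does not follow this: "this approach is not taken here with Mean POEM for questions with non-missing responses computed instead". The model uses Mean POEM. The severity categories (0–2, 3–7, 8–16, 17–24, 25–28) and the shift tables use Total POEM. No missing-item rule is stated for Total POEM, and no minimum number of answered items is set for either questionnaire.

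**The forms.** The POEM form (protocol Appendix 7) tells patients "Please leave blank any questions you feel unable to answer". The DLQI form (Appendix 6) asks patients to check that every question is answered.

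**The concern.** The SAP gives the item mean as its substitute for the cited rules, but the mean does not reach every output. Where a total is still reported, a skipped item is treated as if the patient had no problem with it. That is a small approximation for one blank item. It is a poor one for two, three or more, which is where the cited rules would withhold the score.

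At stake is the reading of the descriptive quality-of-life and symptom tables. A patient whose disease has not changed can move to a milder POEM category, or lose several DLQI points, by leaving items blank. If blanks were more frequent in one arm, these tables would show a difference between arms that does not exist.

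**Working it through.** **Inputs.** DLQI has 10 items scored 0–3, with a blank scored 0 (SAP 2.2.12.3, protocol 9.1.5). POEM has 7 items scored 0–4 (protocol 9.1.6, SAP 2.2.12.3), with the SAP's severity bands.

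**Maximum scores in the plan.** DLQI 10 × 3 = 30 and POEM 7 × 4 = 28. Both match the documents.

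**What a blank adds to Total POEM.** This has to be inferred. The SAP defines Mean POEM as Total POEM divided by the number of items answered. That is a mean only if the total is the sum of the answered items, so a blank adds 0.

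**Unchanged symptoms, k items blank.** For a patient with the same score s on every item, Total = s × (number of items − k) and Mean = Total ÷ (number of items − k) = s.

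| Scale | s | k | Total, complete form | Total with blanks | Mean |
|---|---|---|---|---|---|
| POEM | 4 | 1 | 28, very severe | 6 × 4 = 24, severe | 4.0 |
| POEM | 4 | 3 | 28, very severe | 4 × 4 = 16, moderate | 4.0 |
| POEM | 3 | 2 | 21, severe | 5 × 3 = 15, moderate | 3.0 |
| POEM | 2 | 4 | 14, moderate | 3 × 2 = 6, mild | 2.0 |
| DLQI | 2 | 2 | 20 | 8 × 2 = 16 (−4) | 2.0 |
| DLQI | 2 | 3 | 20 | 7 × 2 = 14 (−6) | 2.0 |

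The first row, with one POEM item blank, is what the cited rule itself gives. In every other row the cited rules would leave the form unscored. For the totals, then, the departure matters only from two blanks upwards.

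**Sub-scales.** A two-item DLQI sub-scale scored 3 + 3 = 6 becomes 3 with one item blank. The cited whole-form rule does not cover this case.

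**Two outputs that disagree.** With only one POEM item answered, scored 2, the total is 2 and the category is clear or almost clear. Mean POEM is 2 ÷ 1 = 2.0, which on the full scale is 2.0 × 7 = 14, moderate.

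**Direction.** Take POEM with every item at 3. Complete at one visit and two blanks at the next reads 21 → 15, a false improvement. Two blanks first and then a complete form reads 15 → 21, a false worsening.

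**Selective skipping.** Take POEM items 4, 4, 4, 2, 2, 2, 2: total 20, mean 20 ÷ 7 = 2.86. Skipping two 4s gives total 12 and mean 12 ÷ 5 = 2.40. Skipping two 2s gives total 16 and mean 16 ÷ 5 = 3.20. The total falls both times; the mean can move either way.

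**Mean DLQI denominator.** Data management scores the DLQI and supplies it in the SDTM datasets (SAP 2.1, 2.2.12.3). If blanks are kept as missing, the seven-item example gives 14 ÷ 7 = 2.0. Only if zeros overwrote the item values would it be 14 ÷ 10 = 1.4.

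**The case against.** The strongest reply is that the inferential analyses already handle blanks sensibly. The models use item means over answered questions, and in the constant-score examples the mean does not move at all. This stands. A reader might infer that the modelled DLQI and POEM comparisons also count blanks as zero. The SAP does not support that, because it prescribes a denominator of non-missing responses. A reader might go further and infer that the DLQI denominator will always be 10 because data management assigns zeros. The SAP does not say that item-level missing values are discarded, and its own formula needs them. What remains is a missing sentence, not a demonstrated error.

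A second reply is that the item mean is not on the protocol's scale. On complete forms this is only a rescaling: Mean × 10 and Mean × 7 return the 0–30 and 0–28 scores, and tests are unchanged. It is a matter of presentation. Moving the model to totals with one blank scored 0 would be a step backwards, since it would bring the same understatement into the model (28 → 24 for an all-4 POEM, 20 → 18 for an all-2 DLQI).

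A third reply is that zero for an unanswered DLQI item is prespecified in the protocol and that the SAP is open about departing from the instrument rules. Both are true. Neither supplies a limit on how many blanks a reported total may contain.

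**Conclusion.** The point holds for Total DLQI, the DLQI sub-scale totals, and the POEM severity categories and shift tables. With two or more blanks the totals understate severity whenever the skipped items would have scored above 0. The loss can reach two POEM bands (28 to 16 with three blanks) or 6 DLQI points (20 to 14 with three blanks). A sub-scale can lose half its value with one blank.

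The conclusion rests on these conditions:

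- The zero for a blank is explicit for DLQI but inferred for POEM.
- A reader might infer that blanks always look like improvement. They do so only if there are more of them at the later visit; more at the earlier visit hides improvement or suggests worsening. The POEM shift tables name Week 8, the last treatment visit and Week 8 to Week 10, and do not clearly name baseline.
- Bias between arms needs skipping that differs by arm. The documents give no skip rate, so the number of affected forms is unknown.
- The modelled means are free of the zero-scoring problem provided item-level missing values are kept. Selective skipping can still move them in either direction.

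DLQI and POEM are exploratory, the affected outputs are descriptive, and the primary and secondary endpoints are untouched. This is a minor point.

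**What to change.** In SAP 2.2.12.3:

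1. Apply the cited not-scored rule (two or more items unanswered) to Total DLQI, and to Total POEM before any severity category or shift table is formed.
2. Report a DLQI sub-scale total only when both of its items are answered.
3. State that unanswered items stay missing at item level in SDTM, so that the denominators of Mean DLQI and Mean POEM are correct.
4. Keep the mean scores in the models, and show the results also as Mean × 10 (DLQI) and Mean × 7 (POEM), so that they can be read on the 0–30 and 0–28 scales.

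In protocol 9.1.5, add the same limit to the rule that scores an unanswered DLQI question as 0.

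The cost is a few lines of SAP and protocol text and a small change to the derivations. The downside is that a few incomplete questionnaires become unscored in the descriptive tables. The modelled analyses lose no forms.
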